8.2. Assessment of Safety

8.2.1. Specification of Safety Variables

Safety assessments will consist of monitoring and reporting adverse events (AEs) and serious adverse events (SAEs) that are considered related to any of the study treatments (intravitreal dexamethasone pellet (Ozurdex); intravitreal methotrexate; intravitreal ranibizumab (Lucentis), all events of death, and any study specific issue of concern.

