3.1. Type of study

- Randomized, three-arm, parallel design, randomized comparative effectiveness trial
- Randomization stratified by presence or absence of concomitant systemic corticosteroid and/or immunosuppressive therapy for any indication
- Unit of randomization is patient, not eye; if both eyes meet eligibility criteria, both receive same treatment
- Allocation ratio (1:1:1)
- Multicenter
- Fixed sample size, 240 (80 per treatment group)
- Anniversary close-out at the 6-month clinic visit
- Reading center graders and visual acuity examiners will be masked to treatment
- Treating physicians and patients will be unmasked (the intravitreal therapies are different in appearance and have potentially different injection schedules)

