8.1. General overview

Adverse events (AEs) will be recorded on study data forms and submitted to the CC. Serious adverse events (SAEs), which include death, all hospitalizations, life-threatening illness, overdose, or congenital abnormalities in the offspring of subjects, will be reported to the CC as SAE reports within 72 hours after clinical center personnel become aware of the event. An assessment will be made by the clinical investigator at the managing clinical center as to whether the event is related to treatment. [name], the CC Safety Officer, and [name], the DSMC Safety Officer, have been commissioned to review all adverse events and to make recommendations to the DSMC as to any actions that may be needed. All SAEs will be reported expeditiously regardless of the relationship of treatment. These reports will be sent to the CC Medical Safety Officer for immediate review and determination as to whether the event meets the criteria for a safety report. Any SAE reports of a subject death will be sent to DSMC Medical Safety Officer within 24 hours of receipt at the CC. Non-death SAE reports will be sent to the DSMC Medical Safety Officer within 7 days of receipt at the CC. The DSMC Medical Safety Officer will review each report to determine what, if any, additional actions are needed, including whether the other DSMC members need to be informed of the event immediately as opposed to waiting for the next DSMC meeting or conference call. All serious and unexpected events possibly related to study treatment will be reported as safety reports to the NEI project officer, the FDA, the pharmaceutical supplier (where appropriate), and all clinical centers in accordance with FDA regulations. The CC and clinical centers will submit all safety reports as expedited reports to their IRBs. Reports of AEs not deemed to be unexpected will be submitted to the CC IRB, to the IRB of the clinical center in which the event was reported, as well as to any other study center IRBs which require such reports.

Specific adverse event reporting requirements and instructions are detailed in the MERIT Manual of Procedures.

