8.2.2. Adverse Events

An AE is any unfavorable and unintended sign, symptom, or disease temporally associated with the use of an investigational medicinal product (IMP) or other protocol-imposed intervention, regardless of attribution.

This includes the following:

- AEs not previously observed in the subject that emerge during the protocol-specified AE reporting period, including signs or symptoms associated with uveitic macular edema that were not present prior to the AE reporting period.
- Complications that occur as a result of protocol-mandated interventions.

If applicable, AEs that occur prior to assignment of study treatment associated with medication washout, no treatment run-in, or other protocol-mandated intervention.

Preexisting medical conditions (other than the condition being studied) judged by the investigator to have worsened in severity or frequency or changed in character during the protocol-specified AE reporting period.

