8.3. Methods and timing for assessing and recording safety variables

The clinical center investigator is responsible for ensuring that all AEs and SAEs that are observed or reported during the study, are collected and reported to the Coordinating Center and their governing IRB. The Coordinating Center is responsible for reported events to the FDA, appropriate IRB(s), and Genentech, Inc. in accordance with CFR 312.32 (IND Safety Reports).

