8.3.2. Assessment of Adverse Events

- All AEs and SAEs whether volunteered by the subject, discovered by study personnel during questioning, or detected through physical examination, laboratory test, or other means will be reported appropriately.
- Each reported AE or SAE will be described by its duration (i.e., start and end dates), regulatory seriousness criteria if applicable, suspected relationship to the study treatment (see following guidance), and actions taken.
- To ensure consistency of AE and SAE causality assessments, investigators should apply the following general guideline:

- Yes
 - There is a plausible temporal relationship between the onset of the AE and administration of the study treatment, and the AE cannot be readily explained by the subject's clinical state, intercurrent illness, or concomitant therapies
- And/or
 - The AE follows a known pattern of response to the study treatment; and/or the AE abates or resolves upon discontinuation of the study treatment or dose reduction and, if applicable, reappears upon re-challenge.
- No
 - Evidence exists that the AE has an etiology other than the study treatment (e.g., preexisting medical condition, underlying disease, intercurrent illness, or concomitant medication):
- And/or
 - The AE has no plausible temporal relationship to study treatment administration (e.g., cancer diagnosed 2 days after first dose of study treatment).

Expected adverse events are those adverse events that are listed or characterized in the Package Insert or current Investigator Brochure.

Unexpected adverse events are those not listed in the Package Insert (P.I.) or current Investigator Brochure (I.B.) or not identified. This includes adverse events for which the specificity or severity is not consistent with the description in the P.I. or I.B. For example, under this definition, hepatic necrosis would be unexpected if the P.I. or I.B. only referred to elevated hepatic enzymes or hepatitis.

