8.6. Additional Reporting Requirements for IND Holders

The Coordinating Center holds the IND for MERIT and is responsible for the following.

For Investigator-Sponsored IND Studies, some additional reporting requirements for the FDA apply in accordance with the guidance set forth in 21 CFR § 600.80.

Events meeting the following criteria need to be submitted to the Food and Drug Administration (FDA) as expedited IND Safety Reports according to the following guidance and timelines:

7 Calendar Day Telephone or Fax Report:

The Investigator is required to notify the FDA of any fatal or life-threatening adverse event that is unexpected and assessed by the investigator to be possibly related to the use of a study treatment. An unexpected adverse event is one that is not already described in the study treatment Investigator Brochure. Such reports are to be telephoned or faxed to the FDA and Genentech within 7 calendar days of first learning of the event.

15 Calendar Day Written Report

The Investigator is also required to notify the FDA and all participating investigators, in a written IND Safety Report, of any serious, unexpected AE that is considered reasonably or possibly related to the use of a study treatment. An unexpected adverse event is one that is not already described in the study treatment investigator brochure.

Written IND Safety reports should include an Analysis of Similar Events in accordance with regulation 21 CFR § 312.32. All safety reports previously filed by the investigator with the IND concerning similar events should be analyzed and the significance of the new report in light of the previous, similar reports commented on.

Written IND safety reports with Analysis of Similar Events are to be submitted to the FDA, Genentech, and all participating investigators within 15 calendar days of first learning of the event. The FDA prefers these reports on a Medwatch 3500 form, but alternative formats are acceptable (e.g., summary letter).

FDA fax number for IND Safety Reports:

Fax: [name]

All written IND Safety Reports submitted to the FDA by the Investigator must also be faxed to Genentech Drug Safety:

[contact] or [contact]

*And to the Site IRB**For questions related to safety reporting, please contact Genentech Drug Safety:*

[contact]

[contact] or [contact]

*IND Annual Reports**Copies to Genentech:*

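### Section 8.2.1 restricts safety assessments to events judged related to treatment, contradicting 8.1 and 8.3 to 8.3.2; if followed, it could filter non-serious AE reports differently by arm

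*Combined protocol and SAP*

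**What the plan says.** Section 8.2.1, which specifies the safety variables, says the assessments will consist of "monitoring and reporting adverse events (AEs) and serious adverse events (SAEs) that are considered related to any of the study treatments". It adds every death and any trial-specific matter of concern, neither of which depends on attribution. A non-fatal event judged unrelated is therefore out of scope unless it falls under the second, undefined category.

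The neighbouring sections are wider:

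- Section 8.1 has AEs recorded on study forms without a relatedness condition, and says of serious events: "All SAEs will be reported expeditiously regardless of the relationship of treatment".
- Section 8.2.2 defines an AE as something temporally associated with the study drug or another "protocol-imposed intervention, regardless of attribution".
- Section 8.3 makes the clinical center investigator "responsible for ensuring that all AEs and SAEs that are observed or reported during the study, are collected and reported" to the Coordinating Center.
- Section 8.3.1 makes reporting of all AEs and SAEs mandatory during the reporting period. Attribution limits reporting only after that period ends.
- Section 8.3.2 lists suspected relationship among the items that describe each reported event.

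The clinical investigator makes the relatedness assessment (8.1). Section 3.1 states: "Treating physicians and patients will be unmasked".

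**The concern.** Section 8.2.1 carries the title under which a reader would look up what counts as a safety variable, and 8.3 then describes how safety variables are assessed and recorded. A coordinator or analyst could reasonably take 8.2.1 as setting the scope of what 8.3 collects. Section 9.2 compares AE rates between arms without saying whether the counts are all-cause or related-only, so nothing in the analysis section settles the question.

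If the narrow rule were followed, an event would be counted only after someone who may know the treatment had judged its cause. That judgement can depend on the drug. One route to a positive causality assessment in 8.3.2 is that the event fits a known response to the study treatment, and the lists of known responses differ by arm. The trial's objective (2.1) weighs effectiveness against tolerability, so an AE comparison shaped by prior belief about each drug would weaken half of the intended conclusion.

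**Working it through.** The plan states no figure on this point, so the check is a comparison of texts, followed by one line of algebra.

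**Step 1. Is the conflict real and current?** Take a non-fatal, non-serious AE that the investigator judges unrelated.

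- Under 8.2.1 it is not part of the safety assessments, unless it is treated as a trial-specific concern.
- Under 8.1 it is recorded and sent to the Coordinating Center.
- Under 8.3 and 8.3.1 it must be collected and reported.
- Under 8.3.2 it is reported with its relationship entered as an attribute.

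The first result is incompatible with the other three. For a non-fatal SAE judged unrelated, 8.2.1 conflicts with the same sections. It also conflicts with 8.4.11, which sends SAEs unrelated to ranibizumab to the Coordinating Center within three days. The conflict with 8.2.2 is weaker, because 8.2.2 defines an AE and does not set a reporting rule. All of this is in the body of the protocol, not in the revision history.

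**Step 2. Could the restriction act differently by arm?** Treating physicians are unmasked (3.1), and the clinical investigator assigns relatedness (8.1). Take cataract. Section 7.1 lists cataract development as an effect of the dexamethasone implant. Sections 7.2 and 7.3 do not list cataract for methotrexate or ranibizumab. Section 7.4 lists only iatrogenic traumatic cataract, as a rare risk of the injection in any arm. The same finding could be attributed to treatment in one arm and to underlying disease in another.

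**Step 3. What form would the bias take?** Let λ₁ and λ₀ be the true AE rates in two arms, and r₁ and r₀ the probabilities that an event is judged related. If only related events are counted:

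- expected counted rate in each arm = λ × r
- apparent rate ratio = (λ₁/λ₀) × (r₁/r₀)

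The bias factor is r₁/r₀. It equals 1 when attribution is the same in both arms. The documents give neither r₁ nor r₀, so any number put here would only restate an assumption.

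**Step 4. Which outcomes are exposed?**

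- *Safety outcomes in 3.5* (IOP thresholds, vitreous hemorrhage, retinal tear or detachment, endophthalmitis, loss of 15 or more letters): not exposed. None carries a relatedness condition, and the schedule in 3.8 has tonometry, acuity and an ophthalmic exam at every visit.
- *SAEs*: protected by 8.1, which has them reported whatever the attribution and reviewed by the Coordinating Center's Medical Safety Officer.
- *Cataract*: exposed. The abstract names it as an adverse-event outcome, but 3.5 defines no cataract measure and 3.8 lists no lens grading, so its comparison may rest on AE reports.
- *Non-serious systemic events*: exposed, for the same reason.

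**The case against.** The strongest reply is that 8.2.1 is one loosely worded scope sentence, outweighed by operative rules that agree with one another. Sections 8.1, 8.3, 8.3.1 and 8.3.2 all point to full collection. Section 9.2 states no related-only filter, and neither does the description of monitoring committee reports in 11.2. Section 8.1 also defers detailed reporting instructions to the Manual of Procedures, which is not available here and may settle the matter. This stands as a limit on the consequence: the documents do not plan a related-only comparison. It does not remove the contradiction, because a sentence that specifies the safety variables still says the opposite of the sections around it.

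A reader might infer more, and the documents do not support it:

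- *That the IOP comparison is compromised.* The IOP outcomes in 3.5 are defined by measured thresholds, so attribution cannot alter them.
- *That an unexpected SAE in a participant also taking systemic methotrexate would escape expedited review because concomitant therapy explains it.* Section 8.1 sends every SAE to the Medical Safety Officer, who determines whether it qualifies as a safety report. The 15-day rule in 8.6 covers a "serious, unexpected AE that is considered reasonably or possibly related to the use of a study treatment" and names no assessor; investigator assessment appears only in the 7-day rule for fatal or life-threatening events.
- *That the Yes/No causality test in 8.3.2 is itself an error, because 8.1 and 8.6 refer to events possibly related.* Section 8.3.2 calls itself a general guideline. Its routes to a positive answer are alternatives as well as cumulative, so failing the one about "clinical state, intercurrent illness, or concomitant therapies" does not force a negative answer. The etiology route to a negative answer requires that evidence of another cause exists, not merely that one is plausible. A graded scale is a preference, not a correction.

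**Conclusion.** The contradiction holds and should be corrected. Its practical consequence is a risk that the text leaves open, not a stated plan to compare related events only. That risk is confined mainly to non-serious AE reports, with cataract the clearest case.

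The size of any bias cannot be given. It depends on three things the documents do not settle: whether any site or analyst applied 8.2.1 in place of 8.1 and 8.3, whether attribution differed between arms, and what the Manual of Procedures says. If all events were collected and 9.2 is run on all of them, there is no bias from this source.

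**What to change.** In 8.2.1, delete the clause that limits AEs and SAEs to those considered related to a study treatment. State instead that the safety variables are all AEs and all SAEs whatever their attribution, with the investigator's relatedness assessment recorded for each. The existing mention of deaths and trial-specific concerns can stay.

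In 9.2, state that AE rates are compared using all recorded events, with related-only events as a secondary display at most. No change to 8.3.2 is needed for this point.

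The cost is a few words in two sections. The only downside is slightly more AE recording at any site that had been working to 8.2.1.

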8.2.2. Adverse Events

An AE is any unfavorable and unintended sign, symptom, or disease temporally associated with the use of an investigational medicinal product (IMP) or other protocol-imposed intervention, regardless of attribution.

This includes the following:

- AEs not previously observed in the subject that emerge during the protocol-specified AE reporting period, including signs or symptoms associated with uveitic macular edema that were not present prior to the AE reporting period.
- Complications that occur as a result of protocol-mandated interventions.

If applicable, AEs that occur prior to assignment of study treatment associated with medication washout, no treatment run-in, or other protocol-mandated intervention.

Preexisting medical conditions (other than the condition being studied) judged by the investigator to have worsened in severity or frequency or changed in character during the protocol-specified AE reporting period.

8.2.3. Serious Adverse Events

An AE should be classified as an SAE if the following criteria are met:

- It results in death (i.e., the AE actually causes or leads to death).
- It is life threatening (i.e., the AE, in the view of the investigator, places the subject at immediate risk of death. It does not include an AE that, had it occurred in a more severe form, might have caused death.)
- It requires or prolongs inpatient hospitalization.
- It results in persistent or significant disability/incapacity (i.e., the AE results in substantial disruption of the subject's ability to conduct normal life functions).
- It results in a congenital anomaly/birth defect in a neonate/infant born to a mother exposed to the IMP.
- It is considered a significant medical event by the investigator based on medical judgment (e.g., may jeopardize the subject or may require medical/surgical intervention to prevent one of the outcomes listed above).

8.3. Methods and timing for assessing and recording safety variables

The clinical center investigator is responsible for ensuring that all AEs and SAEs that are observed or reported during the study, are collected and reported to the Coordinating Center and their governing IRB. The Coordinating Center is responsible for reported events to the FDA, appropriate IRB(s), and Genentech, Inc. in accordance with CFR 312.32 (IND Safety Reports).

8.3.1. Adverse Event Reporting Period

- The study period during which all AEs and SAEs must be reported begins after informed consent is obtained and initiation of study treatment [or "initiation of any study procedures"] and ends 30 days following the last administration of study treatment or study discontinuation/termination, whichever is earlier.
- After this period, investigators should only report SAEs that are attributed to prior study treatment.

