3.5. Secondary outcomes

- Rates of IOP elevation of ≥ 24 mm Hg, ≥ 30 mm Hg, and ≥ 10 mm Hg from baseline during the 24 weeks of follow-up
- Percent change in macular thickness as measured by OCT over the 24 weeks of follow-up
- Proportion of eyes with macular edema events over the 24 weeks of follow-up
 - $\geq 20\%$ reduction in macular thickness (or normalization of macular thickness even if there is $<20\%$ reduction)
 - "Resolution", defined as normalization of the macular thickness, i.e., <260 μm on the standard scale Worsening defined as a 20% increase in macular thickness from the lowest value after an injection
 - "Recurrence" defined as $>20\%$ increase in the central subfield measurement on OCT to an abnormal value in an eye that previously had resolution of ME
- Mean change in BCVA over the 24 weeks of follow-up.
Best-corrected visual acuity score will be measured at every study visit under standardized lighting conditions by certified study examiners masked to study treatment using logarithmic (ETDRS) visual acuity charts, according to the method described by Ferris, et al.¹²⁷
- Safety outcomes including elevated IOP (>30 mm Hg thresholds); vitreous hemorrhage; retinal tear/detachment; endophthalmitis; severe vision loss (≥ 15 Early Treatment Diabetic Retinopathy Study [ETDRS] letters) during the 24 weeks of follow-up.

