3.8. Data collection schedule

Visit ID	M01	M02	M03	M04	M05	M06	M07
Time	Baseline	4-wk	8-wk	12-wk	16-wk	20-wk	24-wk
Medical/ophthalmic history	X	X	X	X	X	X	X
Treatment history	X	X	X	X	X	X	X
Best-corrected visual acuity	X	X	X	X	X	X	X
Tonometry	X	X	X	X	X	X	X
Ophthalmic exam	X	X	X	X	X	X	X
Gonioscopy	X						
OCT	X	X	X	X	X	X	X
Health utility measures (EuroQOL, VFQ-25)	X	X	X	X	X	X	X
Adverse event monitoring	X	X	X	X	X	X	X
Pregnancy testing	X [†]	X [‡]	X [‡]	X [‡]	X [‡]	X [‡]	X [‡]

[†] Required for all women of childbearing potential at M01

[‡] Required for women of childbearing potential before any additional intravitreal injections of methotrexate or ranibizumab

4. Treatment schedule

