8.4.3. Deaths

All deaths that occur during the protocol-specified AE reporting period, regardless of attribution, will be reported to the appropriate parties. When recording a death, the event or condition that caused or contributed to the fatal outcome should be reported as the single medical concept. If the cause of death is unknown and cannot be ascertained at the time of reporting, report “Unexplained Death”.

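### Section 8.3.1 ends AE and SAE reporting 30 days after the last study injection, against sections 3.8, 8.3 and 8.4.8; if followed, reporting time depends on arm and response

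*Combined protocol and SAP*

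**What the plan says.** Protocol section 8.3.1 sets one period for required reporting of all AEs and SAEs. That period "ends 30 days following the last administration of study treatment or study discontinuation/termination, whichever is earlier". What follows is narrower: "After this period, investigators should only report SAEs that are attributed to prior study treatment".

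Other current sections set a different scope or time:

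- **3.8 (data collection schedule):** the row "Adverse event monitoring" is marked at all seven visits, weeks 0 to 24, without distinction by arm.
- **8.3:** the site investigator must ensure that "all AEs and SAEs that are observed or reported during the study, are collected and reported".
- **8.4.8:** reporting of attributed SAEs alone applies once a participant has finished or left the study, not 30 days after an injection.
- **8.1:** "All SAEs will be reported expeditiously regardless of the relationship of treatment". No end date is given.
- **8.2.1 and 8.4.3:** 8.2.1 counts every death within the safety assessment, although for other events it speaks only of those thought to be treatment-related. Section 8.4.3 limits deaths to the 8.3.1 period: "All deaths that occur during the protocol-specified AE reporting period, regardless of attribution, will be reported to the appropriate parties".
- **9.2:** AE rates are compared between arms with a negative binomial model. Neither an AE window nor an offset for time at risk is stated.

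No section says which rule prevails. Section 8.1 defers: "Specific adverse event reporting requirements and instructions are detailed in the MERIT Manual of Procedures". That manual is not among the documents.

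**The concern.** A reporting period tied to the last injection does not have a fixed length in this trial, because the number and timing of injections differ by arm and by response. Ranibizumab is required at weeks 0, 4 and 8, subject to the pre-injection IOP limit (4.2.4). Dexamethasone at week 8 (4.2.2) and methotrexate at weeks 4 and 8 (4.2.3) are given only if the retreatment criteria in 4.2.5 are met. From M04 onward, retreatment in every arm is conditional. A participant whose edema clears early, or whose IOP rules out another injection, therefore has a shorter reporting period than one who keeps being injected.

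The objective in 2.1 weighs tolerability alongside effectiveness, so the AE comparison in 9.2 matters. Under 8.3.1 it would rest on reporting time that is unequal and related to outcome. The documents' own background adds to this: section 1.6 puts the dexamethasone pellet's effect at about 5 months (3 to 4 months in later case series), whereas a participant given one pellet would leave full AE reporting after 30 days.

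**Working it through.** The plan states no figure for the length of the reporting period, so this is date arithmetic on its schedule.

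**Inputs.** Visits at weeks 0, 4, 8, 12, 16, 20 and 24 (3.8), that is days 0, 28, 56, 84, 112, 140 and 168. Reporting ends 30 days after the last study injection (8.3.1). Follow-up closes at the 6-month visit, M07 (3.1). First injection is taken on day 0.

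**Formula.** With L the day of the participant's last study injection in either eye, the part of follow-up covered is min(L + 30, 168). A post-baseline AE-monitoring visit is outside if its day is later than L + 30.

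| Last injection | L + 30 | Follow-up covered | Post-baseline visits outside |
|---|---|---|---|
| M01 (day 0) | 30 | 30/168 = 18% | 5 of 6 |
| M02 (day 28) | 58 | 58/168 = 35% | 4 of 6 |
| M03 (day 56) | 86 | 86/168 = 51% | 3 of 6 |
| M04 (day 84) | 114 | 114/168 = 68% | 2 of 6 |
| M05 (day 112) | 142 | 142/168 = 85% | 1 of 6 |
| M06 (day 140) | 170 | 168/168 = 100% | 0 of 6 |
| M07 (day 168) | 198 | 168/168 = 100% | 0 of 6 |

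**By arm, on the fewest injections the schedule calls for:**

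- Dexamethasone or methotrexate, one injection: day 30.
- Ranibizumab, weeks 0, 4 and 8: day 86.

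**Sensitivity.** Sections 4.2.2 to 4.2.4 allow the first injection up to 10 days after randomization. A single injection on day 10 moves the close from day 30 to day 40 (40/168 = 24%), still with 5 of 6 visits outside. The phrase about whichever event comes first can be read two ways: the 30 days may attach to the last injection only, or also to discontinuation/termination. Both readings give the same end date for a participant who completes follow-up and was last injected at M05 or earlier. They can differ only in whether reporting runs past week 24 after an M06 or M07 injection.

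**Which data are exposed.** Tonometry, acuity and the ophthalmic exam are scheduled at every visit to week 24 in all arms (3.8), and attributed SAEs stay reportable (8.3.1, 8.4.8). What falls outside is mainly non-serious AEs, SAEs not attributed to treatment, and, through 8.4.3, deaths.

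**The case against.** The strongest reply is that the rule can hardly be applied as written. Retreatment is permitted at every visit from M04 to M07 (4.2.1), so a site cannot know on day 30 or day 86 that the last injection has already been given. Section 8.4.1 asks for consistent AE elicitation at all evaluation time points, and history is taken at each visit. Sites may simply follow 3.8, and the Manual of Procedures may say so. Also, 8.3.1 is a subsection of 8.3 and could be read as defining what 8.3 means by the study period.

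Much of this stands. It lowers the likelihood that events are really lost. It does not reconcile 8.3.1 with 3.8 or with 8.4.8, and a cutoff applied in retrospect, for instance when the AE data set is assembled, would give the same unequal windows.

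Four stronger readings are tempting but unsupported:

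- **That 86 against 30 days measures a distortion of the AE comparison.** Section 9.2 compares rates, not counts. With an offset and constant event rates, unequal length alone would not bias the comparison. The documents give no retreatment frequency, and many participants with persistent edema may be retreated.
- **That reporting closes by day 86 for anyone moved to other treatment at M04.** Section 4.2.1 still permits the assigned drug at M05 to M07.
- **That the window closes eye by eye.** Reporting is per participant, so an injection in either eye extends it.
- **That the safety outcomes in 3.5 are lost.** IOP and severe vision loss come from scheduled measurements, and scheduled exams may detect the other ocular events listed there. The conflict with 3.5 is weak.

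**Conclusion.** The contradiction is in the current text and should be fixed. The clearest conflicts are with 3.8, 8.3 and 8.4.8; for unattributed SAEs and deaths there is also a conflict with 8.1 and 8.2.1. Followed literally, 8.3.1 gives nominal windows from day 30 (one dexamethasone or methotrexate injection) through day 86 (minimum ranibizumab course) to the full 168 days. These figures assume nominal visit days and a first injection on day 0.

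The consequence for the AE comparison is conditional on 8.3.1 being applied, by sites or at analysis. The size and direction of any bias cannot be determined: the guaranteed minimum window is longest for ranibizumab, but participants in any arm who keep needing injections have longer windows. An offset for reporting time would handle unequal length under constant rates; it would not remove the dependence on response. The primary outcome and the outcomes measured at scheduled visits are untouched.

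**What to change.** 1. Amend 8.3.1 so that all AEs and SAEs are reported for every participant through the week-24 visit (M07) or earlier study discontinuation. Keep reporting of attributed SAEs alone for the time after that, as 8.4.8 has it.
2. Align 8.2.1 (scope of events, all deaths) and 8.4.3 (period for deaths) with that rule.
3. State whether reporting continues for 30 days after an injection at M06 or M07.
4. In 9.2, compare AE rates over the common period, with time at risk as the offset.
5. Check that the Manual of Procedures gives the same period.

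The cost is one wording amendment and somewhat more AE forms at visits already scheduled. If reporting is extended after an M06 or M07 injection, those participants need one contact after close-out. Nothing in treatment changes.
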